### 11.1 Unexpected Adverse Events

An unexpected AE, the nature, severity, specificity, or outcome of which is not consistent with the summary of product characteristics described in the Product Insert

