### 11.2 Events Not to be Considered an Adverse Event

Pre-existing medical conditions/signs/symptoms present 30 days prior to the Screening Period that do not worsen in severity or frequency during the study are defined as Baseline Medical Conditions, and are not to be considered AEs. Anticipated day-to-day fluctuations of pre-existing conditions, including the disease under study, that do not represent a clinically significant exacerbation or worsening need not be considered AEs.

Not to be Considered an SAE are Hospitalization for:

- A standard procedure for protocol therapy administration. However, hospitalization or prolonged hospitalization for a complication of therapy administration will be reported as an SAE.
- Routine treatment or monitoring of the studied indication not associated with any deterioration in condition.
- A procedure for protocol/disease-related investigations (e.g., surgery, scans, endoscopy, sampling for laboratory tests, bone marrow sampling). However, hospitalization or prolonged hospitalization for a complication of such procedures remains a reportable SAE.
- Hospitalization or prolongation of hospitalization for technical, practical, or social reasons, in the absence of an AE.
- A procedure that is planned (i.e., planned prior to starting of treatment on study); must be documented in the source document and the eCRF. Hospitalization or prolonged hospitalization for a complication remains a reportable SAE.
- An elective treatment of a pre-existing condition unrelated to the studied indication.
- Emergency outpatient treatment or observation that does not result in admission, unless fulfilling other seriousness criteria above.

If an AE is considered serious, both the AE page/screen of the eCRF and the SAE Report Form must be completed.

For each SAE, the investigator will provide information on severity, start and stop dates, relationship to investigation product, rationale of the causality, the action taken regarding IP, and outcome.

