### 11.3 Serious Adverse Events

An SAE is any AE, occurring at any dose level/regimen and regardless of causality that:

- Results in death.
- Is life-threatening: Life-threatening means that the Subject was at immediate risk of death from the reaction as it occurred (i.e., it does not include a reaction that hypothetically might have caused death had it occurred in a more severe form).
- Requires inpatient hospitalization or prolongation of existing hospitalization; however, a hospitalization for an elective procedure will not be considered an SAE.
- Results in persistent or significant disability/incapacity. An AE is incapacitating or disabling if the experience

results in a substantial and/or permanent disruption of the subject's ability to carry out normal life functions.

- Is a congenital anomaly/birth defect: Congenital anomaly/birth defect in a child of a subject or its partner that was exposed to study drug prior to conception or during pregnancy.
- Other, is an important medical event: An important medical event is an event that may not result in death, be life-threatening, or require hospitalization but may be considered an SAE when, based upon appropriate medical judgment, it may jeopardize the Subject and may require medical or surgical intervention to prevent one of the outcomes listed in the definitions for SAEs. Examples of such medical events include allergic bronchospasm requiring intensive treatment in an emergency room or at home, blood dyscrasias, or convulsions that do not result in inSubject hospitalization, or the development of drug dependency or drug abuse.

For the purposes of reporting per regulations, any suspected transmission of an infectious agent via a medical product is by default a suspected unexpected serious adverse reaction (SUSAR) and should be reported in an expedited manner

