#### **11.5 Relationship to Study**

The investigator must determine the relationship between the administration of study drug and the occurrence of an AE/SAE as Not Suspected or Suspected as defined below. Factors for the assessment of causal relationship include, but are not limited to, the temporal relationship between the AE and the administration of study drug, known side effects of study drug, concomitant therapy, course of the underlying disease and pertinent study procedures.

- Not Suspected: Means a causal relationship of the AE to study drug administration is unlikely or remote, or other medications, therapeutic interventions, or underlying conditions provide a sufficient explanation for the observed event
- Suspected: Means there is a reasonable possibility that the administration of study drug caused the AE. "Reasonable possibility" means there is evidence to suggest a causal relationship between the study drug and the AE.

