### 20.3 Appendix 3: Mitigation of Side Effects

- All side effects will be recorded as AEs or SAEs and reported accordingly
- AE and SAE will be inquired about in both phone conversations and in the Subject Diary
- Auditory
  - Tinnitus and deafness
    - Subjects experiencing either of these symptoms will be referred to their primary care physician for treatment.
- Dermatological
  - Rash or pruritis, including Vesiculobullous rash or Maculopapular rash
    - Subject will be prescribed appropriate treatment depending on the type of rash or pruritis
  - Photosensitivity reaction
    - Subject will be advised to avoid sunlight for the duration of treatment. If Subject must go out, they should wear pants and long sleeves.
  - Stevens-Johnson syndrome, DRESS syndrome, TEN
    - Subject will be referred to a hospital for evaluation treatment
  - Urticaria
    - Will be treated with antihistamines and observed. If this treatment is not effective, the Subject will be re-evaluated by PI for further treatment and/or referral
  - Dermatitis including exfoliative dermatitis
    - Subject will be evaluated by the PI and treatment will be initiated based on the type of dermatitis. Therapies could include topical hydrocortisone cream, antihistamines, and glucocorticoids
  - Dry Skin
    - Subject will be provided with a skin care recommendation depending on the degree of severity
  - Hyperhidrosis
    - Subject will be referred to their PCP for evaluation
  - Eczema
    - Subject will be provided with topical treatment if necessary
  - Erythema multiforme
    - Subject will be observed, as this condition usually resolves without treatment. The efficacy of glucocorticoids in this condition is debated
  - Fungal dermatitis
    - Subject will be prescribed appropriate antifungal medication
  - Pigmentary changes in skin and mucous membranes
    - Usually reversible upon discontinuation of medication
  - Bleaching of hair
    - Usually reversible upon discontinuation of medication
  - Alopecia
    - If severe, medication may be discontinued. This condition is usually reversible upon discontinuation of medication
  - AGEP
    - Usually reversible upon discontinuation of medication
  - Outbreak of psoriasis, occasionally associated with fever and hyperleukocytosis
    - Subject will be prescribed appropriate therapy depending on type and severity of symptoms
  - Angioedema

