#### 20.4 Appendix 4: Subject Stopping Criteria

- QT interval >500msec
- Increase in QT >30-60msec
- Presence of torsades de pointes
- Occurrence of unexpected drug related SAE
- Any other risk which the Investigator deems necessary to discontinue the study drugs

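### Appendix 4 requires study drug to stop for SAEs as a class only when a drug-related SAE is unexpected; a labelled one is largely left to the investigator's discretion

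*Combined protocol and SAP*

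**What the plan says.** Appendix 4 (Section 20.4) gives five grounds for stopping a subject's drug: QT above 500 msec, a QT increase, torsades de pointes, "Occurrence of unexpected drug related SAE", and any other risk for which the investigator thinks a stop is needed.

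Section 11.1 defines an unexpected AE as one "the nature, severity, specificity, or outcome of which is not consistent with the summary of product characteristics described in the Product Insert". Section 11.5 rates an event as Suspected when "there is a reasonable possibility that the administration of study drug caused the AE". Section 11.3 defines an SAE. Among other criteria, it counts an event that "Requires inpatient hospitalization or prolongation of existing hospitalization", and it gives "convulsions that do not result in inSubject hospitalization" as an example of an important medical event. Section 11.2 asks the investigator to report, for each SAE, the "rationale of the causality, the action taken regarding IP, and outcome".

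Appendix 3 (Section 20.3) sets out the management of individual side effects. Some entries state that drug will be discontinued. Others give only treatment or referral. For SJS, DRESS and TEN the whole instruction is "Subject will be referred to a hospital for evaluation treatment".

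**The concern.** Whether a reaction is in the label decides how it is reported. It is a poor test of whether a seriously harmed subject should take the next dose. As written, a Suspected SAE of a kind and severity already in the insert falls outside the only mandatory SAE criterion, while an unfamiliar one falls inside it.

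Detection is not the problem. Appendix 3 says that "AE and SAE will be inquired about in both phone conversations and in the Subject Diary", and the Schedule of Events has the EKG worn continuously. The problem is what must happen next. Subjects dose at home from a shipped supply, and several of these reactions send them to a hospital or specialist. At that point no protocol rule requires the study drug to stop.

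**Working it through.** No sample size, power or rate enters this point, so the check compares the texts.

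**Step 1: what Appendix 4 requires.** Of the five criteria, three concern QT or torsades, one concerns SAEs as a class, and one is discretionary (3 + 1 + 1 = 5). The SAE criterion needs two conditions together: drug related and unexpected. A Suspected SAE that agrees with the insert in nature, severity, specificity and outcome fails the second condition. Section 11.1 also refers to a single insert, although the regimen has several products.

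**Step 2: which reactions are likely to count as expected.** The insert is not available, so listing in Section 13.1 serves as the proxy. That section lists risks by drug, and the distinction matters.

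**Step 3: whether Appendix 3 closes the gap.**

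| Reaction | Listed in 13.1 under | Appendix 3 instruction | Stop stated? |
|---|---|---|---|
| SJS/DRESS/TEN | both drugs | hospital referral | no |
| Angioedema (Dermatological) | both drugs | hospital if severe, otherwise medication | no |
| Angioedema (Hypersensitivity) | both drugs | airway management and medication | no |
| Hepatic failure group | hydroxychloroquine: fulminant hepatic failure; azithromycin: hepatic failure, fulminant hepatitis, necrosis | referral for hospitalization | no |
| Seizure/convulsion | both drugs | neurology referral | no |
| Anaphylaxis | azithromycin only | epinephrine, hospitalization if necessary | no |
| Pancreatitis | azithromycin only | hospital evaluation | no |
| Cardiomyopathy | hydroxychloroquine only | no entry | none |
| Hepatitis | azithromycin | discontinue and monitor | yes |
| Bronchospasm | both drugs | discontinue and treat | yes |
| Acute renal failure | azithromycin | discontinue and hospitalize | yes |
| Blurred vision | hydroxychloroquine | discontinue | yes |

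The first seven rows are entries with no stated stop. Hepatitis carries a stop while the hepatic failure entry does not, and bronchospasm carries one while anaphylaxis does not. Across Appendix 3, eight entries state a fixed stop: hepatitis, blurred vision, corneal changes, maculopathy, acute renal failure, interstitial nephritis, bronchospasm and asthma. Four state a conditional one: alopecia, abdominal pain, face edema and raised BUN/creatinine. The appendix therefore does write stops where they are intended.

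**Step 4: whether these reactions are SAEs.** Usually yes, through admission, threat to life or the important-medical-event criterion. It is not automatic. Section 11.3 excludes elective admissions, and Section 11.2 excludes emergency outpatient care without admission unless another seriousness criterion is met. The convulsion example depends on medical judgment.

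**Step 5: what a stop would prevent.** The supply is 20 hydroxychloroquine tablets (2 a day for 10 days) and 6 azithromycin tablets (2 on Day 1, then 1 a day on Days 2 to 5). Take, as an illustration, a reaction after the Day 3 doses. Hydroxychloroquine left: 20 − 3 × 2 = 14 tablets. Azithromycin left: 6 − (2 + 1 + 1) = 2 tablets. After Day 5 only hydroxychloroquine remains to be stopped, and after Day 10 neither drug.

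**The case against.** The strongest reply is that no investigator told of SJS or anaphylaxis would continue the drug, that the last Appendix 4 criterion allows a stop for any risk, and that Section 11.2 requires the action taken to be recorded. Silence in Appendix 3 is not an instruction to keep dosing, and fulminant hepatitis can be read as falling under the hepatitis entry. Courses are short: 5 days for azithromycin and 10 for hydroxychloroquine. All of this limits the harm. None of it supplies a requirement, because recording an action does not oblige anyone to take one.

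Four stronger readings are tempting, and the documents do not support them:

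- A reader might infer that every expected drug-related SAE is left to discretion. The QT and torsades criteria and the Appendix 3 stops apply whether or not the event is expected.
- A reader might infer that all the reactions above are expected for both drugs. By the Section 13.1 proxy, anaphylaxis, pancreatitis or hepatic necrosis attributed to hydroxychloroquine would be unexpected, so the present criterion already requires a stop. A case more severe than labelled would also be unexpected.
- A reader might infer that every hospital referral is an SAE. Sections 11.2 and 11.3 exclude some hospital contacts.
- A reader might count Appendix 3 entries that mention hospital care and find 14, of which 1 (acute renal failure) states a stop. The count is right, but it does not measure this gap. It includes epistaxis, dehydration, and dyspnea or pneumonia that may be COVID-19 itself, and it omits seizure.

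**Conclusion.** The point holds as a missing requirement, not a missing power. The SAE criterion carries a restriction that does not suit its purpose, and Appendix 3 does not make up for it in seven entries on grave reactions. Cardiomyopathy, which Section 13.1 says can be fatal, has no entry there, and the cardiac criteria in Appendix 4 reach only QT and torsades.

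The conclusion rests on one assumption: that listing in Section 13.1 indicates what the insert contains. On that basis the gap is firmest for SJS/TEN/DRESS, angioedema, hepatic failure or fulminant hepatitis, and seizure. For anaphylaxis and pancreatitis it holds only when the event is attributed to azithromycin. Without event rates, no count of affected subjects is possible. The documents do not show that any subject would in fact be kept on drug. It should be fixed because the reactions are severe and the remedy is a matter of wording.

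**What to change.** Replace the fourth Appendix 4 criterion with: *Occurrence of any SAE Suspected (Section 11.5) to be related to hydroxychloroquine, azithromycin or their placebos, expected or not: discontinue hydroxychloroquine and azithromycin (or placebos); stop vitamin C, vitamin D or zinc if Suspected for that product.* Naming the products matters because both arms take the vitamins and zinc to Day 30.

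For consistency, add *hydroxychloroquine and azithromycin (or placebos) will be discontinued* to seven Appendix 3 entries:

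- SJS/DRESS/TEN
- angioedema under Dermatological, if severe
- angioedema under Hypersensitivity, if airway management is needed
- pancreatitis
- the hepatic failure group
- anaphylaxis
- seizure

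Add a cardiomyopathy entry with the same instruction. The Appendix 3 stops would apply without a separate causality rating, as the eight existing fixed stops do.

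The work is one criterion reworded, seven entries amended and one added, with no new visits, tests or staff. The downside is possibly a few more discontinuations.
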